#### **Inclusion Criteria**

- Filipino patients, aged 18-27 years old
- New patients diagnosed with Acne Vulgaris and a Global Acne Grading System score of at least 19
- Able to read and write in English or Tagalog
- Seen at the Out-Patient Department of East Avenue Medical Center Department of Dermatology

#### **Exclusion Criteria**

- Patients with other chronic dermatoses or systemic disease
- Taking oral supplements or medications within the past 4 weeks
- Patients who are pregnant or lactating

### **Study Procedure**

1. In the Dermatology Out-Patient Department of East Avenue Medical Center, new patients who were diagnosed to have Acne Vulgaris, will be screened if they meet the inclusion/exclusion criteria.
2. Informed consent will be obtained for those who are qualified.
3. Patients will be given proper treatment whether they agree to participate or not. Patients who agree to participate will fill out an information sheet and three resident physicians will assess the patient's Global Acne Grading System (GAGS) and acne inflammatory score on initial visit, after 1 month, and after 2 months.
4. Patients will be given the bottle of zinc gluconate or placebo to be taken for 2 months, with patient education and a daily monitoring sheet. Details of blinding and randomization detailed below. Patients will be asked to follow up every 2 weeks where assessment and pill count will be done. Participants will be advised to continue intake if there are any unconsumed capsules within the 60-day period.
5. Data collected will be tabulated by the investigators and data analysis will be done.

### **Definition of Variables**

#### **Treatment arm**

In this study, patients will be randomly assigned to receive either placebo or oral zinc gluconate supplementation. The assignment to a treatment arm was performed randomly.

### Improvement in the disease activity

This will be assessed by determining the difference in the GAGS and inflammatory scores of a patient at the start and at the end of the clinical trial. The GAGS and inflammatory scores will be measured by the same investigators at the start and at the end of the trial. Secondary measures include the examiner's assessment and patient's self-assessment scores at the end of the trial.

### **Randomization**

Allocation to either Group A (Zinc Gluconate) or Group B (Placebo) will be done using a computer-generated block randomization scheme ([www.randomizer.org](http://www.randomizer.org)). The randomization will be done by a resident physician who was not involved in the trial. The randomization codes will be kept in a locked cabinet and will only be broken at the end of the study. Therefore, the assignments will be concealed from both participants and the investigators. The investigator, also blinded, will be the one to dispense the medications to the patients.

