### **Treatment allocation and blinding**

The Solgar Zinc Gluconate 50mg will be repackaged by the TARC Pharmacy Laboratory of the University of Santo Tomas into the clear size 0 capsules. The same laboratory will prepare the placebo capsules and package the cornstarch placebo into the same clear size 0 capsules. This repackaging is necessary to ensure that the physicians and the participants will be blinded during the study. The capsules will be packaged in uniform airtight containers with 60 capsules per container. A third person not directly involved in care and assessment of the subjects, who also did the randomization, will be tasked to encode the capsules into groups A and B. Bottles will be labelled with the corresponding patient number only. Both the physician in charge and the patients will be unaware of which capsules contain Zinc Gluconate or placebo. During the study, patients will be asked to draw a number from 1 to 32, and he/she will get the corresponding bottle. The code will then be revealed during the data analysis portion to allow the statistician to segregate the results into the proper groups.

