### **Intervention**

Patients will be randomly assigned to 60 days of oral Zinc Gluconate capsules (one capsule of 200mg daily) versus the placebo capsules. The participants will be given a container filled with 60 capsules. They will be instructed to take 1 capsule once a day 20 minutes before the morning meal in their residence. The starch placebos will be identical to zinc supplements in size, color, and shape hence both patients and investigators will be unable to tell whether participant will be on zinc supplementation or placebo.

All participants will receive the same adapalene 0.3% + benzoyl peroxide 2.5% preparation to be applied two times a day on affected areas. Patient education on Acne Vulgaris, Zinc sources, and basic skin care will be performed on all patients. Instructions will be given to avoid intake of other medication or supplementation during the 60-day trial.

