### **Stopping Guidelines**

[figure not shown]
Criteria for stopping the intervention include anaphylactic reaction or allergies to the medications, and severe gastrointestinal symptoms. Patients with severe adverse reactions will be treated accordingly to relieve symptoms. They will be considered as "withdrawals" of the study, and still receive proper treatment for acne vulgaris.

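### The randomization code may be opened only at the end of the study, with no visible exception for one patient whose later care after an allergic reaction depends on what the capsule held

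*Combined protocol and SAP*

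**What the plan says.** Two sections of the combined protocol and SAP deal with when the code is opened.

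- Randomization: "The randomization codes will be kept in a locked cabinet and will only be broken at the end of the study".
- Treatment allocation and blinding: "The code will then be revealed during the data analysis portion to allow the statistician to segregate the results into the proper groups". Until then, "Both the physician in charge and the patients will be unaware of which capsules contain Zinc Gluconate or placebo". The bottle label shows only the patient's number, so it does not identify the content.

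The same section describes who prepared the code: "A third person not directly involved in care and assessment of the subjects, who also did the randomization". The Randomization section says this person is a resident with no part in the trial.

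The Stopping Guidelines foresee reactions: "Criteria for stopping the intervention include anaphylactic reaction or allergies to the medications, and severe gastrointestinal symptoms". The stated response is to relieve symptoms, count the patient as a withdrawal and continue acne care. Neither that section nor Dropouts and Withdrawals mentions the code.

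On other exposures, the Intervention section states "All participants will receive the same adapalene 0.3% + benzoyl peroxide 2.5% preparation" and "Instructions will be given to avoid intake of other medication or supplementation during the 60-day trial". The Exclusion Criteria list "Taking oral supplements or medications within the past 4 weeks".

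**The concern.** A double-blind plan normally keeps the code closed but gives a route for opening one patient's assignment when the treating physician needs it. Here the word *only* in the Randomization section makes this more than an omission. Read literally, it bars a single-patient break before the end of the study.

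The plan itself anticipates a situation where the question would arise. After an allergic or anaphylactic reaction, the physician must still choose further acne treatment and advise the patient what to avoid. The capsule and the topical are then the main study-related suspects, and the capsule's content bears on that advice. A patient who took cornstarch could be told to avoid zinc for no reason, and zinc would stay on the list of suspects until the code is opened.

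What is at stake is the quality of later advice to an individual patient. The statistical results are not affected.

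**Working it through.** No power, error-rate or sample-size calculation applies, and the plan gives no figure to reproduce. The check sets the relevant sections side by side.

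**Step 1. Is there an exception anywhere in the visible text?** The sections on ethics, consent, study procedure, randomization, blinding, intervention, compliance, stopping, withdrawals and statistical analysis were read for any early or individual code break. Two statements on timing were found, in Randomization and in Treatment allocation and blinding. Both put the opening at the end of the study or at analysis. Nothing visible allows one patient's code to be opened, says who may ask, or says how a break would be recorded.

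**Step 2. Does acute care need the allocation?** No. The steps in the Stopping Guidelines (stop the intervention, treat the symptoms) are the same whichever capsule was taken.

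**Step 3. Which products are suspects afterwards?** Every patient takes a capsule and uses the same adapalene and benzoyl peroxide preparation. Recent oral medication is an exclusion, and other medication is discouraged during the 60 days. The capsule and the topical are therefore the main study-related candidates.

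**Step 4. What would disclosure settle?**

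| Capsule held | Cleared | Still suspect |
|---|---|---|
| Cornstarch | Zinc | Placebo capsule (cornstarch, shell) and topical |
| Zinc gluconate | Nothing | Zinc capsule and topical |

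Disclosure is informative mainly for a placebo patient, and then only about zinc. In neither row does it identify the cause.

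**Step 5. Which stopping events matter most?** The case is strongest for allergy and anaphylaxis. It is weaker for gut symptoms, because the consent section already attributes nausea to zinc, so advice can be given without the code.

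**Step 6. What could a break expose?** Bottles are numbered individually, so one disclosure does not by itself reveal another. The Randomization section specifies blocks but gives no block size, and with very small blocks one known assignment could allow inference about others. Roles also overlap: investigators examine patients (Ethical Considerations), an investigator dispenses (Randomization) and gives the examiner's score (Final evaluation), and three residents do the GAGS and inflammatory scoring (Study Procedure). A treating physician who learns an assignment may therefore also be someone who scores.

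**The case against.** The strongest case on the other side is that little is lost. The patient is already protected by stopping, symptomatic treatment and continued acne care. The cautious course, avoiding both zinc and the topical, is open without the code. The named harm is forgoing a supplement for a limited time, and the documents show no consequence of that. This stands, and it is why the point is minor.

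A second objection is that an exception may exist out of sight. A figure is missing in the Stopping Guidelines, the study framework figure is not shown, and consent pages were removed. That is possible, so the finding is limited to the visible text. It does not dispose of the point: an exception elsewhere would conflict with the unqualified *only* in the Randomization section and would need a cross-reference.

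A third objection is that overlapping roles make the fix more than a drafting change. This stands in part. It is limited because the Stopping Guidelines class patients with severe reactions as withdrawals, so scoring after a break should be uncommon.

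Three stronger readings are tempting, and the documents do not support them.

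- *Emergency treatment is compromised.* It is not, since the immediate steps do not depend on the arm.
- *Opening the code would show what caused the reaction.* It would not, as the table above shows.
- *The length of the wait shows the point is serious.* If the code opens on 31 July 2019 (an assumption from the conduct period in Study Design), a patient starting on the document date, 19 December 2018, and reacting that day would wait 12 + 31 + 28 + 31 + 30 + 31 + 30 + 31 = 224 days. A patient finishing day 60 on 31 July would wait 0. These are calendar waits under an assumed date. The long end presumes a start before ethics approval, which was still to be sought, and a later analysis would lengthen every wait. They measure neither harm nor probability and should not be used to rank the point.

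**Conclusion.** The point holds as a minor patient-safety improvement. As written, the plan bars any code break before the end of the study and gives no visible exception for a single patient, although it foresees anaphylaxis and allergy. The benefit of an exception is real but partial, and it falls in later care, mainly for a placebo patient from whom zinc could be ruled out. The documents give no rate for such reactions, so no probability is offered. There is no effect on any estimate, error rate or sample size.

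The conclusion rests on two assumptions: that the missing figures and removed pages contain no exception, and that the wording in the Randomization section is followed literally. Confidence is medium because of the first.

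**What to change.** Amend the Randomization section along these lines:

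*Codes are broken only at the end of the study, except that after an event listed in the Stopping Guidelines, where knowing the allocation affects the patient's care, a named code holder outside care and assessment (for example the resident who did the randomization) may disclose that one patient's assignment to the treating physician. Each break is logged and reported. Anyone told the assignment does not score that patient afterwards.*

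The code holder should be named. The plan says who randomized and encoded the capsules, but not who keeps the cabinet or can be reached when an event occurs. If an exception already exists elsewhere, a cross-reference and removal of the unqualified *only* would be enough.

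The cost is a short clause, a log entry per break, and another scorer where the treating physician would otherwise have assessed that patient. The downside is that an occasional patient is unblinded and, with small blocks, a break could allow some inference about other bottles. Limiting disclosure to one assignment and one physician keeps that small. Sample size, significance level and analysis do not change.

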### **Treatment allocation and blinding**

The Solgar Zinc Gluconate 50mg will be repackaged by the TARC Pharmacy Laboratory of the University of Santo Tomas into the clear size 0 capsules. The same laboratory will prepare the placebo capsules and package the cornstarch placebo into the same clear size 0 capsules. This repackaging is necessary to ensure that the physicians and the participants will be blinded during the study. The capsules will be packaged in uniform airtight containers with 60 capsules per container. A third person not directly involved in care and assessment of the subjects, who also did the randomization, will be tasked to encode the capsules into groups A and B. Bottles will be labelled with the corresponding patient number only. Both the physician in charge and the patients will be unaware of which capsules contain Zinc Gluconate or placebo. During the study, patients will be asked to draw a number from 1 to 32, and he/she will get the corresponding bottle. The code will then be revealed during the data analysis portion to allow the statistician to segregate the results into the proper groups.

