### **Checking of Compliance**

Participants will be given a Daily Monitoring Sheet where they can note if they have taken

the capsule for the day, as well as side effects or other remarks. The number of remaining capsules will be checked every 2 weeks during follow-up. Patient will be required to bring medicine bottle on follow-up for the pill count.

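### Both fills go into clear capsule shells, so the blind rests on a powder match that the plan asserts but gives no method to achieve or check

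*Combined protocol and SAP*

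**What the plan says.** Under Treatment allocation and blinding, the active product is to be placed "into the clear size 0 capsules", and the same pharmacy laboratory is to "package the cornstarch placebo into the same clear size 0 capsules". The purpose is explicit: "This repackaging is necessary to ensure that the physicians and the participants will be blinded during the study". Bottles hold 60 capsules in uniform airtight containers and carry only a patient number.

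The Intervention section then states the result expected of this step: "The starch placebos will be identical to zinc supplements in size, color, and shape". It concludes that neither patients nor investigators will be able to tell which product a participant is taking.

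The Randomization section has a blinded investigator dispense the medication. Under Checking of Compliance, remaining capsules are counted every 2 weeks: "Patient will be required to bring medicine bottle on follow-up for the pill count".

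**The concern.** Repackaging is the plan's means of making the two products look the same, yet a clear shell does not hide its contents. The two fills are different substances, a commercial zinc product and cornstarch. Their colour, texture and fill level are what anyone looking at the capsule sees.

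Every outcome is open to expectation. Three resident physicians score the inflammatory and GAGS scores, and the two secondary outcomes are the examiner's assessment and the patient's self-assessment. If those who score could sort patients by capsule appearance, any resulting bias would fall on the between-arm difference. Neither the t-test nor the Mann-Whitney alternative in the Statistical analysis plan could detect or remove it.

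**Working it through.** The plan states no figure for this point, so the check sets the blinding provisions side by side.

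1. **What the shell equalises.** Both arms use the same clear size 0 shell, which fixes outer size and shape. It does not fix what is seen through it.

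2. **What the plan promises about the fill.** The Intervention section says colour will be identical. With a clear shell, that is a commitment about the powder. Texture and fill level are not mentioned, although both would be visible.

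3. **How the promise is met.** No section describes an opaque shell, a colourant, a common excipient, or matching of shade or fill level. None describes an inspection before release or an end-of-trial test of the blind. The match is stated as an outcome, without a procedure.

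4. **What the placebo has to match.** Treatment allocation and blinding says "The Solgar Zinc Gluconate 50mg will be repackaged", while Intervention gives "one capsule of 200mg daily". The two passages must be reconciled. Until they are, the active fill that the placebo must resemble is itself unclear.

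5. **Which safeguards act on appearance.** Locked codes and number-only labels prevent disclosure through paperwork. They do nothing about the look of the capsule. Of the containers the plan says: "The capsules will be packaged in uniform airtight containers with 60 capsules per container". It does not say they are opaque.

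6. **Who can compare capsules.** Each patient draws one bottle and so sees one fill only. Staff see both. There are up to 32 numbered bottles, and a count every 14 days over 60 days gives 60/14 = 4.3, so about four counts per bottle. That is 32 dispensings and roughly 32 × 4 = 128 counts. The plan does not say whether the people counting are also the people scoring.

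**Illustration only.** The documents give no basis for the size of a bias. As a pure assumption, suppose unblinding shifted the between-arm mean change by *b* standard deviations with no true effect. The two-sided 5% t-test with *n* per arm then has 2*n* − 2 degrees of freedom and noncentrality *b*√(*n*/2). The 8 per arm approximates the stated minimum of 15. The 16 per arm is the 32 bottles, assuming an equal split.

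| n per arm | b (assumed) | noncentrality | probability of rejecting |
|---|---|---|---|
| 8 | 0.25 | 0.50 | 7.5% |
| 8 | 0.50 | 1.00 | 15.4% |
| 16 | 0.25 | 0.71 | 10.5% |
| 16 | 0.50 | 1.41 | 27.8% |

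These show how such a test responds to a bias of a given size. They are not estimates of what happens in this trial.

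**The case against.** The strongest reply is that the plan does address the match. It commits to identical colour, gives both preparations to one laboratory, and uses the same shells and uniform containers. This stands as far as it goes: it would be wrong to say that the plan is silent on appearance. What is missing is the method and the check.

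A reader might also infer that the powders look different and that the blind failed. The documents do not support this, because neither powder's appearance is described.

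Two further points limit the route to bias, and both stand. Patients see their capsules daily but have nothing to compare them with. A staff member who noticed two kinds of capsule would still not learn from the label which was zinc, and may not be a scorer. Bias would therefore need several steps: a visible difference, someone noticing it, a belief about which is active, and an effect on scoring. The assumed shifts in the table pass over all of these.

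The objection does not remove the dependence itself. A double-blind design with subjective outcomes is better served by securing or checking indistinguishability than by asserting it.

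**Conclusion.** The point holds as a gap in how the blind is protected. Clear shells make the blind depend on two visible powders looking alike, and the plan asserts that likeness without a method or a verification. It is not a demonstrated failure of blinding, and nothing in the documents allows the bias to be sized.

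The conclusion rests on the text alone: clear shells, different fills, no matching or checking step, and outcomes that are all rater-scored or self-rated. Its practical importance rests on two things that the documents leave open: whether the fills differ visibly, and whether staff who handle bottles also score outcomes. Since the protection is cheap and the analysis could not repair a broken blind, the change is worth making without settling either question.

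**What to change.** In Treatment allocation and blinding, replace the clear size 0 capsules with opaque size 0 capsules of a single colour for both arms. Add one sentence: before release, a person who does not know the assignments and takes no part in outcome scoring confirms that filled capsules from the two arms cannot be told apart. The holder of the codes is not suited to this check, because that person knows which capsules are which.

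An opaque shell hides colour, texture and fill level. It does not equalise weight or rattle, nor conceal the contents of an opened capsule, so the check on filled capsules is still needed. The 50 mg and 200 mg statements should be reconciled at the same time, so that the fill to be matched is defined.

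The cost is a different shell at a repackaging step already planned, plus a brief inspection. Sample size, schedule and analysis are unaffected.

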### Sample Size Computation

The sample size is computed using G\*Power software. The effect size used was based on “Low Doses of Zinc Gluconate for Inflammatory Acne” by Dreno, P et al. (1989). According to this, the inflammatory score was statistically lower in the Zinc group than in the Placebo group at 2nd month of observation with p-value less than 0.02. The computed effect size was 0.6708327, this was used given that there was no effect size convention available in G\*Power for repeated measures between factors (ANOVA, F-test). The computed sample size of 12 (6 per group) was estimated using 0.05  $\alpha$ -level of significance at 80% actual power of analysis. Twenty percent of the computed sample size was added to adjust for the dropout rate. Thus, the minimum required sample size is 15. The sample sizes for power of analysis are shown in Table I.

Power of Analysis	Sample Size	Group 1	Group 2
99%	24	12	12
95%	18	9	9
90%	16	8	8
80%	12	6	6

Table I. Sample sizes for power of analysis

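### Patients draw bottle numbers from 1 to 32, so the planned blocks do not control the order of allocation and arm balance is unprotected if enrolment stops short of 32 (minor; free to fix)

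*Combined protocol and SAP*

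**What the plan says.** The Randomization section states: "Allocation to either Group A (Zinc Gluconate) or Group B (Placebo) will be done using a computer-generated block randomization scheme". It gives no block size. A resident physician outside the trial generates the sequence, the codes are locked away until the end, and the investigator who dispenses is blinded.

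Treatment allocation and blinding describes how a patient receives a bottle. The person who randomised also codes the capsules as A or B. "Bottles will be labelled with the corresponding patient number only". Then "patients will be asked to draw a number from 1 to 32, and he/she will get the corresponding bottle".

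The documents do not say how the 32 bottles divide between the arms, whether a drawn number is removed from the pool, or that bottles leave in sequence.

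Sample Size Computation derives 12 patients, 6 per group, adds 20% for dropout and concludes: "Thus, the minimum required sample size is 15". No section commits to enrolling 32.

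**The concern.** Block randomisation keeps the arms close in size as patients accrue, but only if allocations are used in the order generated. Here the blocks can at most fix which bottle numbers hold zinc and which hold placebo. A lottery decides when each bottle is used. The two sections need reconciling, because a report of block randomisation would not describe how patients were actually assigned.

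What is at stake is balance at a shortfall. The stated minimum of 15 is under half of the 32 bottles (15/32 = 47%), and the trial runs at one centre in a fixed window from December 2018 to July 2019. If enrolment ends early, the arms may be unequal, which costs some precision in a very small trial. A draw also leaves no expected order against which a departure in dispensing would show.

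**Working it through.** **Inputs.** From the documents: 32 bottles, minimum sample 15, two-sided alpha 0.05, and "The computed effect size was 0.6708327". Assumed, because not stated: 16 bottles per arm (from the 1:1 sample size), drawn numbers not reused, the effect size read as Cohen's f, and block size 4 for the comparison.

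**The plan's own figure.** The G*Power between-factors repeated-measures test has noncentrality f²·N·m / (1 + (m − 1)ρ), with 1 and N − 2 degrees of freedom. The plan has m = 3 visits; ρ is not stated. With ρ = 0.3 (assumed) and N = 12: 0.4500 × 12 × 3 / 1.6 = 10.13, which gives power 0.818. The same ρ returns 12, 16, 18 and 24 for 80%, 90%, 95% and 99% power, matching Table I. Dropout: 12 × 1.2 = 14.4, rounded up to 15. The stated minimum reproduces.

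**Imbalance under the draw.** The zinc count A among n patients is hypergeometric: P(A = a) = C(16, a)·C(16, n − a) / C(32, n), and the arm difference is |2a − n|. At n = 15, a 10:5 split or worse means a ≥ 10 or a ≤ 5. The terms for a = 10 to 15 sum to 44,017,040, so the probability is 2 × 44,017,040 / 565,722,720 = 15.6%. A split of 11:4 or worse has probability 3.2%.

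| Patients enrolled | Draw: P(difference ≥ 4) | Blocks of 4 in order: largest difference |
|---|---|---|
| 15 | 15.6% (10:5 or worse) | 1 |
| 16 | 28.9% | 0 |
| 20 | 27.3% | 0 |
| 24 | 22.0% | 0 |
| 28 | 10.1% | 0 |
| 30 | 0 (largest possible is 2) | 2 |
| 32 | 0 (exactly 16:16) | 0 |

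At odd n the difference is odd, so 4 or more means 5 or more. At any other stopping point, blocks of 4 in order leave a difference of at most 2; blocks of 8 would allow up to 4.

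**Cost in power.** With two groups, d = 2f = 2 × 0.6708 = 1.34. For the two-sample t-test on change, the noncentrality is d·√(n₁n₂/(n₁ + n₂)).

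- 8:7: 1.34 × √(56/15) = 2.59, power 0.669.
- 10:5: 1.34 × √(50/15) = 2.45, power 0.620.

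Averaging over all splits the draw can produce, against the most balanced split:

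- n = 15: 0.669 to 0.654
- n = 16: 0.704 to 0.689
- n = 20: 0.810 to 0.802
- n = 24: 0.881 to 0.878

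Under the repeated-measures model above, the n = 15 figures are 0.906 for 8:7, 0.872 for 10:5 and 0.896 on average.

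**The case against.** Much can be said for the plan. A draw without replacement from 16 and 16 is statistically one permuted block of 32. If that was the intended scheme, the draw changes nothing. Even otherwise, part of the restriction survives: at n = 16 the SD of the arm difference is 2.87, against 4.00 under simple randomisation. Thirty-two bottles are prepared, and no section plans to stop at 15, 16 or 20. All of this stands, and it keeps the point minor. It does not remove it, because a single block of 32 gives no protection at a shortfall either.

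Three stronger readings are tempting, and the documents support none of them.

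- **Balance is lost at the final sample size.** If all 32 are enrolled and the bottles are 16/16, the arms are exactly equal, and at 30 they differ by at most 2. Nor does the plan claim balance over time; it only names a block scheme.
- **The draw opens allocation to manipulation.** The codes are locked away, the dispenser is blinded and the label does not show the arm. A redraw could not be steered. What is missing is an audit trail.
- **Unequal arms inflate the t-test's type I error.** Marked inflation needs a 10:5 split, a twofold SD ratio and the larger SD in the smaller arm. Averaged over the draw at n = 15 with one arm at twice the SD, the pooled test's error is about 6.0%, against 4.8% to 6.6% at 8:7. The draw adds almost nothing, and the SAP does not say that the pooled form is meant.

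**Conclusion.** The point holds as a minor, free improvement. The sections on randomisation and on dispensing describe different allocation procedures, and under the one that patients would actually experience, the blocks do not protect balance if enrolment stops before 32. A sizeable imbalance is then fairly likely at intermediate sample sizes, fading to nothing at 32. The expected loss of power is 1.5 percentage points or less. Validity is not in question.

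The imbalance probabilities rest on a 16/16 split and no reuse of numbers. The comparison rests on small blocks, here of 4. The power figures also rest on reading the stated effect size as Cohen's f. If numbers could be drawn again, a patient could draw a bottle already used, a case the text does not cover.

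**What to change.** In Treatment allocation and blinding, replace the draw with a rule that bottles 1 to 32 are dispensed strictly in numerical order of enrolment, following the sequence generated under Randomization, with bottle number and date logged for each patient.

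Ordered dispensing protects balance only if the blocks are small, so also specify that the sequence is generated in small permuted blocks, for example of varying sizes 2 and 4 that total 32. Keep the block sizes in the restricted randomisation record, where blinded staff cannot see them.

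This takes two or three sentences and adds no patients, visits or expense. It leaves blinding as it is, makes the two sections agree and makes any departure in dispensing visible.
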